6.1.1 Adverse Events

An Adverse Event (AE) is any untoward medical occurrence in a subject administered a pharmaceutical product. It does not necessarily have a causal relationship with this treatment.

Seizures should not be considered an AE unless they differ significantly from the subjects' baseline. The onset of a new seizure type, as well as an injury incurred as a result of any seizure should be recorded as an AE.

A SAE is any untoward medical occurrence (whether considered to be related to investigational product or not) that at any dose:

- Results in death

- Is life-threatening
 - This requires that the subject be at a risk of death at the time of the event; it does not refer to an event that hypothetically might have caused death if it were more severe.
- Requires inpatient hospitalization or prolongation of existing hospitalization
 - Hospital admissions and/or surgical operations planned before or during a study are not considered AEs if the illness or disease existed before the subject was enrolled in the study, provided that it did not deteriorate in an unexpected way during the study.
- Results in persistent or significant disability/incapacity
- Is a congenital abnormality/birth defect
- Other medically significant events, which do not meet any of the criteria above, but may jeopardize the subject and may require medical or surgical intervention to prevent a serious outcome listed in the definition above (e.g., blood dyscrasias such as anemia requiring blood transfusion).

An adverse drug reaction (ADR) is defined as all noxious and unintended responses to a medicinal product related to any dose. An unexpected ADR is defined as any adverse reaction, the nature of which is not consistent with the applicable product information.

The Investigator is responsible for recording all AEs observed during the study through the Follow-up Visit. Each AE will be evaluated for duration, severity, frequency, seriousness, and causal relationship to the study treatment. Action taken with the study treatment and outcome will also be recorded.

Definitions for severity and causal relationship to the study treatment are presented below.

Severity

The severity of the AE will be characterized as mild, moderate, or severe according to the following definitions:

- Mild events are usually transient and do not interfere with the subject's daily activities.
- Moderate events introduce a low level of inconvenience or concern to the subject and may interfere with daily activities.
- Severe events interrupt the subject's usual daily activity.

Relationship

The Investigator will assess the causal relationship of an AE to the investigational product and characterize the AE as unrelated, unlikely, possible, probable, or unknown (unable to judge). The following definitions of causality will be used:

- Events can be classified as “unrelated” if there is not a reasonable possibility that the study medication caused the AE.
- An “unlikely” relationship suggests that only a remote connection exists between the investigational product and the reported AE. With this classification, other conditions, including chronic illness, progression or expression of the disease state or reaction to concomitant medication, appear to explain the reported AE.
- A “possible” relationship suggests that the association of the AE with the study medication is unknown; however, the AE is not reasonably supported by other conditions.
- A “probable” relationship suggests that a reasonable temporal sequence of the AE with drug administration exists and, in the Investigator’s clinical judgment, it is likely that a causal relationship exists between the drug administration and the AE. Other conditions (concurrent illness, progression or expression of disease state or concomitant medication reactions) do not appear to explain the AE.

All efforts should be made to classify the AE according to the above categories. The category “unknown” (unable to judge) may be used only if the causality is not assessable (e.g., because of insufficient evidence, conflicting evidence, conflicting data, or poor documentation).

The frequency of each observed event will be recorded. Clinical actions taken as a result of an AEs include pausing, stopping, or delaying dosing of the investigational product. If applicable, the resolution of each observed AE will also be recorded; unresolved AEs at the time of subject discontinuation will be noted as such.

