6.1.1.1 Monitoring of AEs Potentially Related to Drug Metabolism

Cannabidiol inhibits drug metabolism mediated by a subset of CYP proteins (see Section 1.1.2). Thus, the Investigator and study center staff should monitor subjects who are taking concomitant medications that are metabolized by CYP2C19, CYP2C9, or CYP1A1 or by p-glycoprotein with special care. Medication(s) that is/are inhibitor(s) or inducer(s) or sensitive substrates of CYP3A4 should be monitored with special care.

The CYP proteins noted above metabolize a selection of clinically important AEDs. As such, subjects should be monitored for AEs that may be related to a change in the metabolism of background AEDs. These may include:

- Increases in liver enzymes
- Increases in side effects associated with background AEDs
- Development of new side effects associated with background AEDs.

Similarly, several AEDs are known inducers of CYP3A4.²⁴ As such, their use may result in alterations in the level of the investigational product. Plasma levels of cannabidiol and 7-OH cannabidiol will be assessed as described in Section 6.2.

The Investigator may choose to assess plasma levels of background AEDs with which the subject is being treated should AEs arise that may be due to altered metabolism of these medications (see above). As noted in Section 4.3, decisions to alter background AED medications and dosing due to safety concerns will be considered on a case by case basis.

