7.2. MISSING DATA

For safety and efficacy analyses, observed values will be used and no imputation will be made for missing data.

Missing dates for Adverse Events (AEs) and concomitant medications will be imputed using the rule provided in [Appendix 1](#). If the intensity is missing for any AE, its intensity will be classified as Severe in the summary tables. If the assessment of relationship of the AE to study treatment is missing, it will be classified as Related in the frequency table of possible related treatment emergent AEs.

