17.1.1.2. Relationship to Study Medication

Relationship, as indicated by the Investigator, is classed as "unrelated", "unlikely", "possible", "probable" (increasing severity of relationship), or "unknown". A "related" TEAE is defined as a TEAE with a relationship to study medication as a "possible" or "probable" relationship to study medication. TEAEs with a missing relationship to study medication will be regarded as a "probable" relationship to study medication. If a subject reports the same AE more than once within that SOC/ PT, the AE with the worst case relationship to study medication will be used in the corresponding relationship summaries.

Document: C:\Users\q832483\Documents\Insy CSR\Pending\Ready for QC\New folder\Statistical Analysis Plan.docx
Author: [REDACTED] Version Number: V1.0 Final
Version Date: 04APR2017

Template No: CS_TP_BS016 – Revision 3
Effective Date: 01May2012

Reference: CS_WI_BS005

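### The causality wording can push cannabidiol–AED interaction events out of the related-only tables, and the SAP leaves *unknown* causality uncounted and unranked

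*Protocol*

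**What the plan says.** **Rating scale (protocol 6.1.1, Relationship).** Investigators choose among *unrelated*, *unlikely*, *possible*, *probable* and *unknown*.

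- *Unlikely*: the link to the product is no more than remote, and "other conditions, including chronic illness, progression or expression of the disease state or reaction to concomitant medication, appear to explain the reported AE".
- *Possible*: the association is not known, but "the AE is not reasonably supported by other conditions".
- *Probable*: timing and clinical judgment favour a causal link, and "Other conditions (concurrent illness, progression or expression of disease state or concomitant medication reactions) do not appear to explain the AE".
- *Unknown*: "may be used only if the causality is not assessable".

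**Interaction monitoring (protocol 6.1.1.1).** Because cannabidiol inhibits some CYP enzymes, "subjects should be monitored for AEs that may be related to a change in the metabolism of background AEDs". One of the listed examples is "Increases in side effects associated with background AEDs"; another is the appearance of new AED side effects.

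**Analysis (SAP 17.1.1.2 and 7.2).** A related "TEAE is defined as a TEAE with a relationship to study medication as a" *possible* or *probable* one. The four categories from *unrelated* to *probable* are ranked in increasing order, and *unknown* is named after the ranking. When a subject has the same event more than once, the worst relationship is used. For blanks, section 7.2 says "If the assessment of relationship of the AE to study treatment is missing, it will be classified as Related", and 17.1.1.2 sets them to *probable*.

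**Outputs restricted to related events.** These are the drug-related TEAEs (SAP 17.1.1) and one of the three standard AESI tables, related AESIs by maximum severity (SAP 17.1.6).

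**The concern.** The protocol anticipates a specific route to harm: the product changes how a background AED is metabolised, and the patient then has more, or new, AED side effects. On its face such an event is a reaction to a concomitant medication. The causality scale uses exactly that feature to support *unlikely* and to rule out *probable*, and the broader wording of *possible* rules it out as well. The scale does not separate an AED reaction that is independent of cannabidiol from one that cannabidiol brought about.

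The overlap is wide. All subjects are treated adjunctively (protocol 1.2.3). Protocol 1.2 lists irritability and sedation for clobazam, appetite and weight loss for topiramate, weight change for valproic acid, and behaviour and mood problems for levetiracetam. SAP Appendix 2 includes irritability, sedation, decreased appetite, weight increase and decrease, aggression and agitation as events of special interest.

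The second issue is in the SAP alone. It resolves doubt upwards elsewhere: missing severity becomes severe, unclear onset becomes treatment-emergent, and missing causality becomes *probable*. A recorded *unknown*, which the protocol reserves for insufficient or conflicting evidence, gets the opposite treatment by default.

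At stake are the tables a reader would use to see which events were attributed to the product. With no control arm, investigator causality is one of the main routes to that attribution.

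**Working it through.** The documents give no figure to reproduce here. The check is a mapping of definitions, followed by arithmetic for scale.

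**Step 1. Map each rating to the SAP's related set.**

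| Rating | Effect of a concomitant-medication explanation (protocol 6.1.1) | Related (SAP 17.1.1.2)? |
|---|---|---|
| *Unrelated* | Not mentioned; needs no reasonable possibility of causation | No |
| *Unlikely* | Supports this rating | No |
| *Possible* | Excluded if it reasonably supports the event | Yes |
| *Probable* | Excluded if it appears to explain the event | Yes |
| *Unknown* | Not mentioned; only if not assessable | No, by definition |
| Missing | Not applicable | Yes, set to *probable* |

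**Step 2. Test an interaction event.** Take an AED side effect that the investigator believes worsened because cannabidiol slowed the AED's metabolism.

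- *Unrelated* fails, because causation is a reasonable possibility.
- *Unlikely* is half met: an AED reaction explains the event, but the link to the product is not remote.
- *Possible* fails literally, because another condition reasonably supports the event.
- *Probable* fails literally, because a concomitant-medication reaction explains it.
- *Unknown* fails, because the investigator has formed a view.

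No category is fully met, and no rule tells the approximately 10 sites which to choose. If a site chooses *unlikely*, the event misses the related-only tables.

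**Step 3. Compare *unknown* with a blank.** An event rated *unknown* adds 0 to the related count; the same event left blank adds 1. If a subject has one preferred term twice, once *unlikely* and once *unknown*, the worst-case rule gives no answer because *unknown* has no rank.

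**Step 4. Scale.** Protocol 8.1 allows up to 60 + 20 = 80 subjects.

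- One subject: 1/80 = 1.25 percentage points. Within an age category the denominator is smaller, so the step is larger.
- The SAP's cut-off for frequent events: 5% × 80 = 4 subjects.

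For illustration, let *k* subjects have an interaction event of one preferred term and let a share *f* be rated *unlikely* or *unknown*. Both are assumptions; neither is in the documents. The related rate is *k*(1 − *f*)/80.

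| *k* (all-TEAE rate) | *f* = 0 | *f* = 25% | *f* = 50% | *f* = 100% |
|---|---|---|---|---|
| 4 (5%) | 5% | 3.75% | 2.5% | 0% |
| 8 (10%) | 10% | 7.5% | 5% | 0% |
| 16 (20%) | 20% | 15% | 10% | 0% |

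The all-TEAE rate is the same across each row. If the 5% cut-off also applies to drug-related events (the SAP sentence can be read either way), then with *k* = 4 a single such rating takes the term below it: 3/80 = 3.75%.

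**The case against.** A reader might infer that interaction events are bound to disappear and that the main safety result is understated. The documents do not support that, for four reasons.

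- *Unlikely* also requires a remote link to the product. An investigator who has just read section 6.1.1.1 could decide that an interaction does not meet this, read a concomitant-medication reaction as one independent of the product, and choose *possible* or *probable*. This stands as a reason to speak of risk rather than certainty. It does not remove the problem, because the literal text of the two related categories still excludes the event.
- The primary criterion is incidence and severity of TEAEs and SAEs, with no causality filter. The all-TEAE, interruption, discontinuation, SAE and fatal-event tables and the listings keep every event. So do the AESI tables by preferred term and by relationship. This stands in full.
- There is other coverage. SAP 17.1.6 relates somnolence to clobazam use with no stated causality filter, SAP 17.3.1 tabulates marked ALT and AST elevations regardless of cause, and the PK plan stratifies by clobazam. This stands, but the first and last concern one AED, and plasma levels of background AEDs generally are optional under protocol 6.1.1.1.
- *Unknown* is a considered judgment and a blank is an omission, so treating them differently can be defended. That is fair as a principle. However, the SAP offers no such reasoning, does not expressly say that *unknown* is unrelated, and gives it no rank.

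Nor do the documents call altered AED metabolism the main expected harm. Protocol 1.4 lists it with effects on spermatogenesis, FSH and immune responses.

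**Conclusion.** The point holds for the outputs limited to related events: the drug-related TEAEs and the related AESIs by maximum severity. Applied literally, the protocol's definitions can bias these downward for the interaction events that the protocol asks sites to monitor. The SAP's silence on *unknown* works in the same direction and is out of line with its worst-case handling of other gaps.

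The size is not known. It depends on how many interaction events occur and how sites rate them, and the documents give neither. At the maximum enrolment of 80 each reclassified subject is worth 1.25 percentage points. The conclusion assumes that at least some sites apply the definitions as written and that *unknown* is tabulated strictly by the SAP's definition of related.

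**What to change.** 1. **Protocol 6.1.1.** State that a concomitant-medication reaction counts as an alternative explanation only when no interaction with the investigational product is suspected, and that an event suspected to arise from such an interaction is assessed as having a possible relationship to the product.
2. **SAP 17.1.1.2.** Show *unknown* as its own row. Rank it between *unlikely* and *possible* for the worst-case rule. Count it as related in the related-TEAE and related-AESI tables, or at least in a sensitivity version, in line with the rule for missing causality.

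Do not selectively query existing *unlikely* ratings. In an open-label study, prompting sites to revisit only those would move ratings in one direction.

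The cost is a short definition and one SAP line. The related-event percentage becomes somewhat higher. The change history that follows the protocol's references is written in the past tense, so data collection may be over. If so, the first change can serve only as a stated limitation, while the second can still be made at reporting, labelled as a sensitivity analysis.

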6.1.1.1 Monitoring of AEs Potentially Related to Drug Metabolism

Cannabidiol inhibits drug metabolism mediated by a subset of CYP proteins (see Section 1.1.2). Thus, the Investigator and study center staff should monitor subjects who are taking concomitant medications that are metabolized by CYP2C19, CYP2C9, or CYP1A1 or by p-glycoprotein with special care. Medication(s) that is/are inhibitor(s) or inducer(s) or sensitive substrates of CYP3A4 should be monitored with special care.

The CYP proteins noted above metabolize a selection of clinically important AEDs. As such, subjects should be monitored for AEs that may be related to a change in the metabolism of background AEDs. These may include:

- Increases in liver enzymes
- Increases in side effects associated with background AEDs
- Development of new side effects associated with background AEDs.

Similarly, several AEDs are known inducers of CYP3A4.²⁴ As such, their use may result in alterations in the level of the investigational product. Plasma levels of cannabidiol and 7-OH cannabidiol will be assessed as described in Section 6.2.

The Investigator may choose to assess plasma levels of background AEDs with which the subject is being treated should AEs arise that may be due to altered metabolism of these medications (see above). As noted in Section 4.3, decisions to alter background AED medications and dosing due to safety concerns will be considered on a case by case basis.

6.1.2 Reporting of AEs

The AEs and SAEs will be assessed at all study visits. As noted in Section 6.1.6, endpoints for this study include the AE/SAE record for each subject.

At each visit, information regarding AEs will be elicited from subjects by questioning conducted by the study center staff and the subject record will be reviewed with the parent(s)/caregiver(s) at each visit. The AEs and SAEs will be assessed at study visits according to the schedule indicated in Table 1. As noted in Section 6.1.6, endpoints for this study include the AE and SAE record for each subject.

All AEs, regardless of severity or when they occur, are to be recorded on the appropriate AE pages (either serious or nonserious) in the eCRF. The Investigator should complete all the details requested including dates of onset, severity, action taken, outcome, and relationship to the investigational product. Each event should be recorded separately.

Any SAE, including death due to any cause, which occurs during this study, whether or not related to the investigational product, must be reported immediately (within 24 hours of the study center's first knowledge of the event) by fax to the Sponsor or designee.

The Sponsor contact information is listed below:

[REDACTED] RPh

Insy Development Company, Inc.

Telephone: [REDACTED]

Fax: [REDACTED]

Email: [REDACTED]

All SAEs will be recorded on the SAE Report Form, entered into the electronic data capture (EDC) system, and recorded in the source documents. The Investigator must complete, sign, and date the SAE Report Form, check that the data are consistent, and send a copy (within 24 hours, preferably by fax) to the Sponsor or designee list above.

The report will contain as much available information concerning the SAE to enable the Sponsor or designee to file a report, which satisfies regulatory reporting requirements. In addition to the initial 24-hour report, a completed, separate SAE Report Form is to be sent to the Sponsor or designee via fax or mail within 48 hours of the event. These timelines apply to initial reports of SAEs and to all follow-up reports.

Criteria for documenting the relationship to the investigational product, severity, and outcome will be the same as those previously described.

All SAEs that are spontaneously reported within 30 days of a subject's last visit are to be collected and reported as previously described.

The information must include at least the following:

- Investigational product
- Study name and code
- Name, address, fax number, email, and telephone number of the reporting Investigator
- Subject identification number, initials, and demographics (gender and date of birth)
- Clinical event
- Description of the AE, including
 - Date of onset
 - Treatment (drug, dose, dosage form)

- Preliminary classification of causal relationship by the Investigator.
- Measures taken (i.e., action taken regarding investigational product in direct relationship to the AE)
- Outcome
- If the AE was fatal or life-threatening
- Cause of death (and whether or not the death was related to investigational product)
- Autopsy findings (if available).

In the case of fatal or life-threatening events, please also immediately report by telephone to the Sponsor or designee.

Additional follow-up information should be completed on an SAE follow-up form with a copy sent to the Sponsor or designee and the original placed in the SAE section of the eCRF binder.

In medical emergencies, the Investigator should use medical judgment and remove the subject from immediate hazard. The Sponsor or designee will be notified regarding the type of emergency and course of action taken and the procedures for SAE reporting will be followed, if necessary.

During a subject's participation in the study, the Investigator or institution will provide adequate medical care for any AEs, including clinically significant laboratory values related to the study. The Investigator or institution should inform a subject when medical care is needed for an intercurrent illness (clinic, laboratory results, or otherwise) which in the opinion of the Investigator should receive medical follow-up.

6.1.2.1 Reporting of SAEs to Regulatory Authorities and Investigators

The Investigators will be responsible for submission of SAEs as required to their Institutional Review Board (IRB)/Independent Ethics Committee (IEC). The Investigators should provide written documentation of IRB notification for each report to the Sponsor or designee. The Sponsor or designee will ensure that all SAEs are reported to the appropriate regulatory authorities.

Any additional local IRB/IEC reporting requirements for SAEs should be observed by the study center.

The Sponsor or its representative will be responsible for notification to regulatory agencies.

6.1.3 Follow-Up of AEs

Any AEs observed will be followed up to resolution. Resolution means that the subject has returned to a baseline state of health or the Investigator does not expect any further improvement or worsening of the AE. All AEs that occur after the subject completed a clinical study should also be reported to the Sponsor or designee within 30 days of the last administration of the investigational product.

6.1.4 Clinical Laboratory Evaluations

All clinical laboratory tests will be reviewed for results of potential clinical significance throughout the study. The Investigator will evaluate any change in laboratory values. If the Investigator determines a laboratory abnormality to be clinically significant, it is considered a laboratory AE; however, if the abnormal laboratory value is consistent with a current diagnosis, it may be documented accordingly.

The following laboratory tests will be assessed at the time points specified by Table 1.

- Hematology: complete blood count (CBC) with differential, including platelet count, neutrophils, lymphocytes, eosinophils, basophils, monocytes, hemoglobin, and hematocrit
- Serum chemistry: total protein, albumin, creatinine, blood urea nitrogen (BUN), uric acid, total bilirubin, direct bilirubin, alkaline phosphatase, FSH, AST, ALT, glucose, calcium, phosphorus, bicarbonate, chloride, sodium, and potassium
- Urinalysis: specific gravity, pH, color, and presence of white blood cells (WBCs), red blood cells (RBCs), and proteins
- β -hCG in urine (pregnancy test)

LFTs (e.g., albumin, direct and total bilirubin, AST, and ALT) will be closely monitored to identify any damage that could be induced by the investigational product.

Levels of FSH will be monitored as a potential surrogate outcome for gametocyte damage.

Laboratory values outside the reference limits suspected to be of any clinical significance will be repeated. Subjects in whom suspected clinical significance is confirmed will either not be included or if already enrolled will be followed until normalization or for as long as the Investigator considers necessary. Additional laboratory variables may be performed for safety reasons if judged appropriate by the Investigator. Further details are provided in the Laboratory Manual.

